6. MATERIALS AND SUPPLIES

6.1 Study Medication

The study medication supplied by Perrigo Israel Pharmaceuticals, Ltd. will consist of:

Test Product: Ingenol Mebutate Topical Gel 0.015%,
Perrigo [REDACTED]

Reference Product: Picato® Topical Gel 0.015% (Ingenol Mebutate Topical Gel 0.015%),
manufactured by Leo Pharma Inc.

[REDACTED]

Vehicle: Vehicle of test product

Perrigo [REDACTED]

[REDACTED]

6.2 Medication Management

6.2.1 Labeling, Packaging and Distribution

The study medication assigned to each subject number will be determined by a computer-generated randomization schedule. Study medication is labeled and packaged, according to the random code, so that neither the subject nor the investigator can identify the treatment.

[REDACTED]

[REDACTED]

[REDACTED]

6.2.2 Retention Samples

Each investigational site where study medication is dispensed to at least one subject will be required to randomly select one block of study medication [REDACTED] to be maintained as retain samples. The retention samples must be stored under labeled conditions [in a refrigerator at 36°-46°F (2-8°C); excursions permitted to 32°-59°F (0°-15°C)] even after the study has concluded. The investigator will maintain [REDACTED] selected block of study medication for each shipment of study medication received. As per the Code of Federal Regulations Part 21, Section 320.38(e), "Each reserve sample shall be stored under conditions consistent with product labeling and in an area segregated from the area where testing is

[REDACTED]

conducted and with access limited to authorized personnel. Each reserve sample shall be retained for a period of at least 5 years following the date on which the application or supplemental application is approved, or, if such application or supplemental application is not approved, at least 5 years following the date of completion of the bioavailability study in which the sample from which the reserve sample was obtained was used.” The investigator will store the retain sample study medication until such time as notification is received from Perrigo that the samples are no longer required.

6.2.3 Storage and Test Article Accountability

Study articles used to conduct this study will be maintained under adequate security by the investigator or designee. Study test articles will be stored in a refrigerator at a temperature of 36°- 46°F (2-8°C); excursions permitted between 32°- 59°F (0°-15°C) in a secured area. Subjects must be instructed to keep the study medication refrigerated at home. Each investigator site will ensure that the temperature of study drug is monitored and recorded throughout the study. The medication should not be frozen, kept away from heat and kept tightly closed. The investigator will not supply study test articles to any person not enrolled in this study, or to any physician or scientist except those named as sub-investigators.

The clinic personnel at each investigator site will keep a running inventory of study test articles dispensed that will include subject numbers assigned and the date each is dispensed and used. A study medication accountability form will be provided to the investigator to document all medications received, dispensed by and used by each subject. At the conclusion of the study all unused, partially used, and empty containers must be inventoried by the monitor and returned to Perrigo or designee, for destruction, except for the retention samples that must remain at the Investigator site.

6.2.4 Randomization

Randomization will be performed according to a computer generated randomization scheme where the treatment group designation has been assigned to the subject number. The treatment designation will remain blinded until the final database is closed. An independent third party will hold the randomization code throughout the study. The randomization scheme will be a block randomization, with each block of [REDACTED] subjects assigned to Test: Reference: Placebo [REDACTED].

6.2.5 Procedure for Breaking the Blind

The investigator, staff at the study site, study monitors, and data analysis/management personnel are blinded to the subject assignment. In the event of an emergency, the specific subject treatment may be identified by removing the overlay of the blinded label for each subject at each investigator site, which is attached to the study medication log. However, every effort should be made to maintain the blind. **The investigator must not scratch off the occluding layer of the label unless absolutely necessary to provide medical treatment to a subject in an emergency situation. When possible, the investigator site should inform Perrigo**

or designee. The reason for breaking the blind must be clearly documented in the source documentation and eCRFs and the subject discontinued from the study.

7. ADVERSE REACTIONS

The potential adverse reactions of generic Ingenol Mebubate Topical Gel 0.015% are anticipated to be similar to those observed in Picato[®] Topical Gel (Ingenol Mebutate Topical Gel 0.015%). The most common adverse reactions related to treatment with Picato[®] Topical Gel include local skin reactions, application site pain, application site pruritus, application site irritation, application site infection, periorbital edema, nasopharyngitis and headache. Eye disorders, including severe eye pain, eyelid edema, eyelid ptosis, periorbital edema can occur after exposure. Severe local skin reactions such as vesiculation/postulation, erosion/ulceration can occur.

7.1 Departure from the Protocol for Individual Subjects

When an emergency occurs requiring a departure from the protocol for a subject, departure will be only for that subject. In such circumstances, the investigator or other physician in attendance will contact the Medical Monitor or Perrigo by telephone and follow up with a written description within one day. The overseeing IRB should also be notified.

7.2 Definitions

An adverse event (AE) is defined as any untoward medical occurrence in a patient administered a medicinal product and which does not necessarily have to have a causal relationship with this treatment. An adverse event can therefore be any unfavorable and unintended sign (for example, an abnormal laboratory finding), symptom, or disease temporally associated with the use of a medicinal product, whether or not considered related to this medicinal product.

A serious adverse event (SAE) is an adverse event that results in any of the following outcomes:

- death
- life-threatening event (i.e., the subject was, in the opinion of the investigator, at immediate risk of death from the event as it occurred. It does not include an event that, had it occurred in a more severe form, might have caused death)
- requires in-subject hospitalization or prolongs hospitalization
- a persistent or significant disability/incapacity or substantial disruption of the ability to conduct normal life functions
- congenital anomaly/birth defect
- Other adverse events that may be considered serious when, based upon appropriate medical judgment, they may jeopardize the patient or subject or may require medical or surgical intervention to prevent one of the previously listed outcomes.

Immediately Reportable Adverse Events (IRAE): Any serious AE or any AE that necessitates discontinuation of study medication, including pregnancy.

Unexpected Adverse Event: An unexpected event is any adverse drug experience, the specificity or severity of which is not consistent with the current approved product labeling (package insert, Appendix D) for the study medication, the Investigator's Brochure, or as described in the clinical protocol and consent materials.

Intensity of Adverse Events: The maximum intensity of an AE during a day should be recorded on the eCRF. If the intensity of an AE changes over a number of days, then separate entries should be made having distinct onset dates for the changes in severity.

Mild - AEs are usually transient, requiring no special treatment, and do not interfere with subject's daily activities.

Moderate - AEs typically introduce a low level of inconvenience or concern to the subject and may interfere with daily activities, but are usually ameliorated by simple therapeutic measures.

Severe - AEs interrupt a subject's usual daily activity and traditionally require systemic drug therapy or other treatment.

Causal Relationship to Study Medication: The following criteria should be used in assessing the apparent causal relationship of an AE to study medication.

Definitely - The AE:

- follows a reasonable temporal sequence from study medication administration
- abates upon discontinuation of the study medication (dechallenge)
- is confirmed by reappearance of the reaction on repeat exposure

Probably - The AE:

- follows a reasonable temporal sequence from study medication administration
- abates upon discontinuation of the study medication (dechallenge)
- cannot be reasonably explained by the known characteristics of the subject's state

Possible - The AE:

- follows a reasonable temporal sequence from study medication administration
- but that could readily be produced by a number of other factors

Unlikely - The AE:

- follows a reasonable temporal sequence from study medication administration

- could have been produced by either the subject's clinical state or by study medication administration

Not related - The AE:

- does not have a reasonable temporal association with the administration of study medication
- has some other obvious explanation for the event

7.3 Eliciting and Reporting of Adverse Events

The investigator will periodically assess subjects for the occurrence of adverse events. In order to avoid bias in eliciting adverse events, the subject or parent/legally authorized representative should be asked a non-specific question (e.g., "How have you been feeling since your last visit?") to assess whether any AE has been experienced since the last visit. All adverse events (as defined in Section 7.2), either observed by the Investigator or one of his/her medical collaborators, or reported by the participant spontaneously, or in response to direct questioning, will be reported and documented in the source and the study reporting forms. When reporting an adverse event, the Investigator must assign a severity grade to each event and declare an opinion on the relatedness of the event to the study medication or procedure. Serious or unexpected adverse events must be reported to Perrigo **within 24 hours** of when the Investigator first learns of the occurrence of the event.

Adverse events will be documented in source and recorded in a timely manner on eCRFs. Adverse events (i.e., worsening of Actinic Keratosis*) that are identified at the last assessment visit (or the early termination visit), must be recorded on the AE eCRF with the status of the AE noted.

* Worsening of the subject's Actinic Keratosis may be expected from application of the study medication. Therefore, this will only be identified as an adverse event if alternative treatment is required.

Adverse event reporting begins from the signing of informed consent/assent. Worsening of Actinic Keratosis from baseline will be considered a new adverse event and will be documented on the source document and eCRFs. Adverse events should be followed until resolved or 30 days after the final study treatment. In any case, serious adverse events that are not resolved or considered to be chronic within 30 days of the final study treatment must be followed by the investigator until they become resolved or are considered to be chronic (stabilized for at least 30 days). All events that are ongoing at this time will be recorded as ongoing on the eCRF.

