7.3.1 Expedited Reporting Responsibilities of the Study Center

For any serious or unexpected adverse event, Perrigo must be notified **within 24 hours** of when the Investigator first learns of the occurrence of the event. Expedited reporting requirements

for serious adverse events are described below. Adequate information must be collected with supporting documentation to complete a standard report for submission to Perrigo. The adverse event term on the AE eCRF and the SAE report should agree exactly. Special attention should be given to recording hospitalizations and concomitant medications.

Subjects with unresolved adverse event(s) or serious adverse event(s) should be followed by the investigator until the events are resolved, events determined to be chronic or the subject is lost to follow-up. Resolution means the subject has returned to the baseline state of health, or the investigator does not expect any further improvement or worsening of the adverse event. The investigator should continue to report any significant follow-up information to Perrigo up to the point that the event has resolved. Any serious adverse event reported by the subject to the investigator that occurs within 30 days after the last assessment, and are determined by the investigator to be reasonably associated with the use of the study medication, should be reported to Perrigo within 24 hours of when the Investigator first learns of the occurrence of the event.

When reporting a serious adverse event (SAE) the Investigator (or the designated staff) will promptly report any serious adverse event or pregnancy by telephone to [REDACTED] immediately after the investigator becomes aware of the event. An SAE form should be completed and sent by fax, email, or overnight courier to [REDACTED] within 24 hours of knowledge of the event by the site. In many cases, only preliminary information will be available. Appropriate follow up information should be sought (hospital discharge summaries, operative reports etc.) and a follow up SAE report form submitted. A designation of causality from the study medication should always be included with a follow up report. Assess and report the causality of the event.

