7.4 SAE & AEs Requiring Discontinuation of Study Drug, including Pregnancies

ANY SAE, WHICH OCCURS AFTER A SUBJECT HAS ENTERED THE STUDY, WHETHER OR NOT RELATED TO STUDY MEDICATION, MUST BE REPORTED TO [REDACTED] AND PERRIGO IMMEDIATELY (WITHIN 24 HOURS) VIA TELEPHONE OR FACSIMILE. IF INITIALLY REPORTED VIA TELEPHONE, THIS MUST BE FOLLOWED-UP BY A FACSIMILE OF THE WRITTEN SAE REPORT WITHIN 24 HOURS OF THE CALL TO [REDACTED].

Non-serious events that require discontinuation of study medication (including laboratory abnormalities) should be reported to Perrigo immediately and within 1 working day. Subjects who discontinue due to experiencing adverse events should be followed clinically until their health has returned to baseline status, or until all parameters have returned to normal. It is expected that the investigator will provide or arrange appropriate supportive care for the subject.

A subject who experiences a severe adverse event related to study drug will be discontinued from the study.

The notification about any serious adverse event should be directed to:

[REDACTED]

[REDACTED]

[REDACTED]

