7.5 Post Study Adverse Events

7.5.1 Non-serious Adverse Events

Adverse events that are identified at the last assessment visit (or the early termination visit) must be recorded on the AE eCRF with the status of the AE noted.

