7.5.2 Serious Adverse Events

Serious adverse events that are identified on the last assessment visit (or the early termination visit) must be recorded on the AE eCRF page and reported to Perrigo according to the procedures outlined above. Subjects with unresolved previously reported serious adverse events, or any new serious adverse events identified on the last assessment visit, should be followed by the investigator until the events are resolved, or the subject is lost to follow-up. Resolution means the subject has returned to the baseline state of health, or the investigator does not expect any further improvement or worsening of the adverse event. The investigator should continue to report any significant follow-up information to Perrigo up to the point that the event has resolved. Any serious adverse event reported by the subject to the investigator that occurs after the last assessment, and are determined by the investigator to be reasonably associated with the use of the study drug, should be reported to Perrigo.

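### Do the different follow-up end points for non-serious adverse events in Protocol 7.3 and 7.3.1 call for a change to the plan?

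*Protocol*

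**What the plan says.** Section 7.3 of the Protocol gives the general rule: "Adverse events should be followed until resolved or 30 days after the final study treatment". It then provides that "serious adverse events that are not resolved or considered to be chronic within 30 days of the final study treatment must be followed" until they resolve or become chronic, and it closes with "All events that are ongoing at this time will be recorded as ongoing on the eCRF".

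Section 7.3.1, on expedited reporting, states: "Subjects with unresolved adverse event(s) or serious adverse event(s) should be followed by the investigator until the events are resolved". It names two further exits: "events determined to be chronic or the subject is lost to follow-up". It gives no number of days. It also defines resolution to include an event in which the investigator foresees no more change, for better or worse.

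Section 7.4 deals with one class of subject: "Subjects who discontinue due to experiencing adverse events should be followed clinically until their health has returned to baseline status", or until all parameters are normal.

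For the last visit, section 7.5.1 asks only that non-serious events "must be recorded on the AE eCRF with the status of the AE noted". Section 7.5.2 asks for more, but for serious events only: "Subjects with unresolved previously reported serious adverse events, or any new serious adverse events identified on the last assessment visit, should be followed".

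The visit-by-visit procedures (5.12.1 to 5.12.5 and the list in 5.12.6), the schedule table (5.13) and the end of 5.17 are redacted, so they may say more.

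**The concern.** Read side by side, 7.3 and 7.3.1 give one non-serious event two different end points. Under 7.3 a site could close its follow-up 30 days after the last application. Under 7.3.1 the same site would carry on until the event resolved, became chronic or the subject was lost. Section 7.4 looks like a third answer, and it has no exit for a chronic event. The instruction in 7.3 to mark events as ongoing refers to a moment that the text does not name.

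Two things would be at stake. Subjects with similar events could be followed for different lengths of time at different sites. The event end date and outcome, which Protocol 2.2 requires to be recorded, could then mean different things from site to site.

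**Working it through.** There is no stated figure to reproduce. The check is day arithmetic followed by a comparison of the passages.

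**Inputs.** Applications on Days 1 to 3 (Protocol 5.16). Visit 3 on Day 29 ± 3 and Visit 4 on Day 57 ± 2 (Synopsis, Study Visits). A period of 30 days from the final treatment (7.3).

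**Where the 7.3 limit falls.** Limit = last application day + 30.
- Full course: 3 + 30 = Day 33.
- Day 1 only: 1 + 30 = Day 31.
- Visit 4 window: 57 − 2 = Day 55 to 57 + 2 = Day 59.
- Gap from limit to Visit 4, full course: 55 − 33 = 22 to 59 − 33 = 26 days.
- Gap from limit to Visit 4, Day 1 only: 55 − 31 = 24 to 59 − 31 = 28 days.

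**Whether that gap is unobserved.** Visit 3 falls on Days 26 to 32 (29 − 3 to 29 + 3), so after a full course it comes before Day 33. The next scheduled contact is Visit 4. Protocol 3.1 monitors all adverse events at both visits, and 5.11 has the diary reviewed for adverse events at each. No visible text adds a contact between them under 7.3.1. An event open at Visit 3 is therefore looked at again at Visit 4 whichever section a site applies. The 22 to 26 days are not a hole in observation. For a subject who completes the study, the two sections diverge in practice only after Visit 4.

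**Which events are affected after that.**
- Serious events: 7.3 and 7.3.1 both continue to resolution or a chronic state, so there is no material conflict.
- Stable non-serious events: under the definition in 7.3.1 these count as resolved. If the word means the same in 7.3, only events still changing are in dispute.
- Expected non-serious events: 7.3.1 opens with serious or unexpected events. Under 7.2 an event consistent with the labeling or with what the protocol describes is not unexpected, and section 7 lists the common reactions. If the 7.3.1 sentence is read within its heading, these events fall under 7.3 alone.
- Subjects who discontinue because of an adverse event: 7.4 is a rule for that class. A class rule beside a general rule is not a contradiction.

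**Which results could move.** SAP 5.6 counts treatment-emergent events by onset on or after the first dose, tabulates them by severity and relationship, and applies Fisher's exact test to the proportion with any such event in the two active groups. SAP 6.1 handles partial dates for the start date only. Neither uses duration, end date or outcome. The one table that could shift in principle is severity, if a non-serious event worsened after the last visit and only some sites recorded it. That table is descriptive. Treatment is double-blind and subject numbers are assigned in sequence at each center, so uneven follow-up would vary by site and has no evident route to differ by arm.

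**The unanchored moment.** Sections 7.3 and 7.5.1 already require the status of events identified at the last or early termination visit. A data manager has a named visit at which an open event is marked as ongoing.

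**The case for a change.** The strongest case for acting is textual. The 7.3.1 sentence names adverse events and serious adverse events separately. Section 7.5.2 uses much the same sentence restricted to serious events, so the authors narrowed it when they meant to. Reading 7.3.1 as limited to expedited events is possible but not secure, and even then an unexpected non-serious event falls under both sections. The class of events is not empty: 5.10 has application-site pain, pruritus and infection recorded as adverse events. An event first found at Visit 4 is already past the 7.3 limit while 7.3.1 still asks for follow-up. A site that stops at 30 days complies with one section and departs from the other.

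Most of this stands as a description of the wording. Against it, the 30-day limit is itself an inference. Section 7.3 does not say that the earlier of the two points governs. The serious-event sentence that suggests a limit also moves from a recommendation to an obligation and adds a chronic exit, so it may be doing something else. A site that follows the longest rule meets every section. For events found at Visit 4, 7.3 and 7.5.1 already say what to record. What the objection does not show is a result that would change.

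**Conclusion.** The concern is right about the wording and does not carry through to the plan. Two sections state different end points for non-serious events, and no visible text ranks them. They can be satisfied together, they part in practice mainly after Visit 4, and no visible analysis depends on which one a site follows. The effect on the equivalence and superiority analyses and on the any-event comparison is nil. The possible effect on the descriptive severity table is confined to events that worsen after a subject's last visit, and the documents give no basis for counting those.

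This rests on three assumptions: the redacted visit procedures agree with the adverse event monitoring described in 3.1; no redacted analysis uses event duration or outcome; and subjects who leave early have their open events recorded at the early termination visit, as 5.17 and 7.5.1 indicate. For those subjects there is no later Visit 4, so the divergence starts at their last visit.

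The passages should be reconciled when the sponsor next revises the text. Which end point applies is a clinical matter for the sponsor, and no view on it is taken here. As a point about the statistical plan, it is a clarification of wording with no gain to the analysis.
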